8.4. Patient Re-Screening & Re-Testing

8.4.1. Re-Screening

Patients may repeat Screening once to qualify for the study (re-screening must occur at least 2 weeks after the screen fail). In rare circumstances, a second re-screening may be appropriate;

in these cases, the site must consult with the medical monitor for approval. When a patient repeats screening, the patient keeps the same patient number while re-screening procedures are completed. No new patient number is generated, this ensures the patient number during EAGLE will match the one used in the prior qualifying study.

8.4.2. Re-Testing

In rare situations, a specific screening test (eg, BNP) may be repeated if the test value is inconsistent with the patient's medical history and/or is considered by the investigator to be an anomaly. Medical monitor approval must be obtained prior to re-testing any of the eligibility parameters for a patient.

8.5. Discontinuation

Discontinuation refers to a patient's permanent stopping of administration of study drug and all study assessments and visits for a patient, site, or study. Patients have the right to discontinue study drug and withdraw from the study at any time for any reason, without prejudice to their medical care. Furthermore, the investigator may discontinue a patient from study drug and the sponsor may terminate a specific site or the entire study. Consultation with the medical monitor should occur prior to study drug discontinuation and withdrawing a patient from the study. The reason for a patient's discontinuation from study drug or study termination will be recorded in the electronic case report form (eCRF).

Patients who permanently discontinue from study drug will be asked to complete the End-of-Study procedures noted in [Table 5](#), and withdraw from the trial.

If a patient reaches ESKD (defined as the initiation of maintenance dialysis for 12 weeks or more or kidney transplant), the patient must terminate from the study and should complete an end-of-study visit. The investigator should record the ESKD event as an adverse event and document the date of dialysis initiation or kidney transplantation.

The reason for discontinuation will be recorded in the eCRF. Reasons for discontinuation may include the following. The standardized disposition term is provided, and details are listed in [brackets]:

- ADVERSE EVENT [Occurrence of an AE or change in medical status that will lead the investigator to be concerned about the patient's welfare];
- DEATH;
- LOST TO FOLLOW-UP [Patient lost to follow-up];
- NON-COMPLIANCE WITH STUDY DRUG [Subject has not agreed with or followed the instructions related to the study medication];
- OTHER [Other specified reason for patient discontinuation];
- PHYSICIAN DECISION [Specified medical reason for patient discontinuation];
- PREGNANCY [Females who become pregnant during the study];
- PROTOCOL DEVIATION [Non-compliance with protocol];

- **PROTOCOL-SPECIFIED WITHDRAWAL CRITERIA MET** [Reached ESKD (initiation of maintenance dialysis for 12 weeks or more or kidney transplant)];
- **STUDY TERMINATED BY SPONSOR** [Sponsor termination of the study];
- **SITE TERMINATED BY SPONSOR** [Premature termination or suspension of an investigational site];
- **WITHDRAWAL BY SUBJECT** [Administrative reasons (eg, inability to continue); Voluntary withdrawal; Withdrawal of consent];

Patients should temporarily interrupt study drug and the medical monitor should be contacted to discuss if permanent study drug discontinuation is required if any of the following occur. Refer to Section [9.1.2](#) for additional guidance

- ALT or AST > 8X ULN;
- ALT or AST > 5X ULN for more than 2 weeks;
- ALT or AST > 3X ULN and (total bilirubin > 2X ULN or International Normalized Ratio [INR] > 1.5);
- ALT or AST > 3X ULN with the appearance of fatigue, nausea, vomiting, right upper quadrant pain or tenderness, fever, rash, and/or eosinophilia (> 5%).

9. TREATMENT OF PATIENTS

9.1. Select Management Guidelines

The following guidelines apply to the management of study participants:

9.1.1. Management of Fluid Status

Specific risk mitigation procedures will be employed to reduce the potential for bardoxolone methyl-induced fluid overload. Laboratory data will be used to monitor fluid status after enrollment. Patients who experience a BNP > 100 pg/mL that represents a doubling (or more) of BNP levels from Day 1 should have an unscheduled telephone contact immediately. If fluid retention is suspected, the patient should be instructed to stop taking study medication immediately and be medically evaluated by the investigator or a local physician within 1 to 2 days.

Additionally, after enrollment and starting study treatment, patients will be closely monitored for rapid weight gain suggestive of fluid overload. Patients will be given a Sponsor-provided scale to use at home to collect and record their weights daily during the first 8 weeks of the treatment period and weekly thereafter. In the event the Sponsor-provided scale is temporarily unavailable (eg, subject is traveling, replacement scale has not arrived to subject, etc.), subjects may use any available scale. Use of a scale other than the Sponsor-provided scale should be documented in the subject diary. During the first 8 weeks, patients who experience a five-pound (2.3 kg) or greater increase in weight in one week or 3 pounds (1.4 kg) in one day should have an unscheduled telephone contact immediately. Whether prompted by BNP elevations, sudden weight gain, or by the presence of clinical signs and symptoms the patient must be instructed to stop taking their study medication immediately and be medically evaluated by the investigator or a local physician within 1 to 2 days.

Investigators are encouraged to start or increase doses of diuretics (thiazides, loop diuretics) early after recognition of edema. This can be done concurrently with temporary drug interruption and re-initiation. Patients may not restart their study medication until the investigator has completed and documented an assessment of fluid overload.

After Week 8, patients who experience a five-pound (2.3 kg) or greater increase in weight in one week will be instructed to return to the clinic for an unscheduled physical examination and laboratory assessment by the investigator. Study medication should not be interrupted until the investigator has completed and documented an assessment of fluid overload.

Investigators should advise patients to watch for signs and symptoms of fluid overload. Patients should be informed to notify their physicians immediately if they experience swollen feet, chest pain, shortness of breath with mild exertion or while lying down, or other relevant symptoms. The investigator should immediately assess symptoms of fluid overload and determine appropriate medical management, as necessary, including whether stopping drug administration is required. At the earliest sign of worsening or new onset peripheral edema or other signs and symptoms of acute volume overload, investigators will be expected to report if changes to a patient's diuretic regimen have been required to manage edema.

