9.8. Serious Toxicities

In the case of serious toxicities, the investigator may choose to interrupt treatment with bardoxolone methyl. Dose reductions are permitted to manage tolerability issues. Patients who resume therapy after an interruption will follow the originally planned study schedule.

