9.9.5. Weight and Body Mass Index (BMI)

Weight must be measured as indicated in Table 5. BMI will be calculated in the eCRF each time the weight is recorded. The Sponsor will provide each patient with a scale to use at home to measure weight, and a diary will be provided to record the at-home weight measurements.

Weights recorded in patient diaries will not be entered in the eCRF. Weights should be taken at approximately the same time each day and recorded in a patient diary. During the first eight weeks, weights will be recorded daily; weekly weights will be recorded thereafter. Patients will be instructed to stop administering study drug and contact the investigator if their daily weight increases per the criteria outlined in Section 9.1.1. Patients will be provided instructions within the Informed Consent Form and/or Assent Form to help ensure consistent weight collection throughout the study.

Weight should be recorded in kilograms, and where weight is measured in pounds, the following formula should be used to convert pounds to kilograms:

$$\text{Weight (in pounds)} \div 2.205 = \text{Weight (in kilograms)}$$

Any conversions of units should be documented in the source documents.

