9.9.11. Telephone Contact

Patients will be contacted by telephone as indicated in Table 5. Patients will be asked about their body weight and other signs of fluid retention, as well as AEs and any changes to concomitant medications. If fluid retention is suspected, the patient should be instructed to stop taking study medication immediately and be medically evaluated by the investigator or a local physician within 1 to 2 days, as detailed in Section 9.1.1.

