5.2. Resuming or Dose-escalating IP after Interruptions or Changes

Patients who interrupt study drug due to a positive COVID-19 test may resume study drug without an in-clinic visit, at the investigator's discretion, if COVID-19 symptoms are mild.

When the investigator deems that it is safe for the patient to return to the site for an in-person visit, the investigator should conduct an evaluation to determine whether the patient is still eligible to receive IP and to determine the appropriate dose. This should include a confirmation that the reason for interruption was not a per protocol specified reason and that the patient's circumstances have not changed in a manner that would prohibit administration of the investigational drug (eg, the patient is now taking an excluded medication). Once the investigator determines IP administration is appropriate, dosing may proceed as recommended in the table below.

IP Status	Dosing Recommendation
IP temporarily interrupted for any reason (eg, COVID-19, delays in obtaining safety lab, AEs)	Resume IP at last administered dose
IP dose not escalated as required per COVID-19 mitigation plan	Continue last administered dose; consider escalating dose, if appropriate
IP de-escalated for any reason (eg, due to delays in obtaining safety labs, AEs)	Continue last administered dose; consider escalating dose, if appropriate

If the patient is not at the target dose, dose escalation to a higher dose is permitted. Patients who dose escalate must have a telephone call 1 week after dose escalation and an office in-clinic visit (or unscheduled visit, if necessary) 2 weeks (\pm 3 days) after dose escalation to collect clinical chemistry, BNP, and NT-proBNP. Unscheduled visits due to dose escalation should also include assessments detailed in Section 9.6 of the protocol. Once the target dose has been reached and 2-week follow-up completed, the Schedule of Assessments may be resumed.

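### After Week 8, a patient who resumes after more than 14 days off drug, or restarts at 5 mg after a liver interruption, is not returned to the first-8-weeks weight rules of Protocol 9.1.1

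*Protocol*

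**What the plan says.** **Weighing.** Protocol 9.1.1 asks patients "to collect and record their weights daily during the first 8 weeks of the treatment period and weekly thereafter". Section 9.9.5 repeats it: "During the first eight weeks, weights will be recorded daily; weekly weights will be recorded thereafter". Adolescents are the exception: 9.1.10 has them weigh daily with no week limit, but its alert is for a loss of more than 3 lb.

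**Weight gain, first 8 weeks.** A gain of 5 lb (2.3 kg) in a week or 3 lb (1.4 kg) in a day calls for immediate telephone contact, and "the patient must be instructed to stop taking their study medication immediately", with medical evaluation within 1 to 2 days.

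**Weight gain, after Week 8.** Only the 5 lb weekly gain is named. It brings the patient to clinic, and "Study medication should not be interrupted until the investigator has completed and documented an assessment of fluid overload".

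**Resuming.** For an extended interruption (more than 14 days is the example given), 7.3.3 has the site agree starting dose and visit frequency with the medical monitor. It requires an evaluation before dosing, a call at about 1 week and a visit at 2 weeks. Section 9.1.2 restarts liver interruptions at 5 mg and sends re-titration to 7.3.2, which adds a call at 1 week and a visit at 2 weeks after each step up. Section 9.8, under serious toxicities, says: "Patients who resume therapy after an interruption will follow the originally planned study schedule". Appendix 1, Section 5.2 recommends "Resume IP at last administered dose" after a temporary interruption, and ties its own follow-up to escalation: "Patients who dose escalate must have a telephone call 1 week after dose escalation".

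None of these sections mentions home weights or weight triggers.

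**The concern.** The tight weight rules are tied to time since the start of EAGLE, not to time since drug was last started. Section 5.1.2.1 reports that heart failure admissions in the Stage 4 CKD trial often followed a fast gain of several kilograms soon after treatment began. It places the excess risk in the first 3 to 4 weeks. Weight is therefore an early warning that the protocol itself relies on.

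A patient who has been off drug for weeks and starts again may be in a similar position, but has the looser rules. The restart after acute dialysis in 9.1.9 shows the stake most clearly. The patient may have been off drug for almost 12 weeks and may still have an eGFR of 15 or below, and 5.1.2.1 says fluid retention is likelier with more advanced renal dysfunction. Such a patient is seen at least every 4 weeks (plus or minus 2) with weight and BNP, but does not regain the first-8-weeks weight rules.

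**Working it through.** No power or sample-size figure is involved. The check compares the rules and then counts what each pathway requires.

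**Units.** With the divisor in 9.9.5, 5 / 2.205 = 2.27 kg and 3 / 2.205 = 1.36 kg, which agree with the stated 2.3 and 1.4 kg.

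**Home weights, adult.**
- 4 weeks: 4 × 7 = 28 daily against 4 weekly, a difference of 24.
- 8 weeks: 8 × 7 = 56 daily against 8 weekly, a difference of 48.
- Longest interval between planned weights: 1 day against 7 days.
- Adolescents: no difference (28 and 28; 56 and 56).

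**Required contacts, counted from the day drug is started or resumed.**
- Start of EAGLE (Table 5): calls on Days 3, 10, 21, 31, 38 and 45; visits on Days 7, 14, 28, 42 and 56. Each visit has a BNP draw.
- 5 mg restart, assuming 2-week steps and the follow-up in 7.3.3 and 7.3.2: calls on Days 7, 21 and 35 and visits on Days 14, 28 and 42 to reach 20 mg. Reaching 30 mg adds a call on Day 49 and a visit on Day 56.
- Resumption at unchanged dose (7.3.3): call on Day 7, visit on Day 14.

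| | Start of EAGLE | 5 mg restart | Unchanged dose |
|---|---|---|---|
| Contacts to Day 28 | 3 + 3 = 6 | 2 + 2 = 4 | 1 + 1 = 2 |
| BNP draws to Day 28 | 3 | 2 | 1 |
| Longest time without required contact, to Day 28 | 7 days | 7 days | 28 − 14 = 14 days |
| Contacts to Day 56 | 6 + 5 = 11 | 6 (20 mg) or 8 (30 mg) | 2 |
| BNP draws to Day 56 | 5 | 3 or 4 | 1 |
| Weight-gain triggers | 2 | 1 | 1 |

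These counts leave out 24-weekly visits that happen to fall in the window and any visits the medical monitor adds. In the re-titrated restart, contacts in the first 4 weeks are spaced no wider than at the start, so the difference that matters there is in the weight rules. At unchanged dose, required contact also ends at Day 14.

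**What passes without a trigger.** After Week 8, a one-day gain from 1.4 kg to just under 2.3 kg prompts nothing unless it forms part of a 2.3 kg weekly gain.

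**What the added contacts capture.** Section 9.9.11 says of telephone contacts: "Patients will be asked about their body weight and other signs of fluid retention". It is written for the calls in Table 5; applying it to the week-1 call after resumption is reasonable but not stated. The 9.6 list for resumption visits includes BNP and vital signs but names neither weight nor diary review. Section 9.9.6 defines vital signs without weight, whereas 9.1.9 and SAP 8.5 include it.

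**The case against.** **Recurrence of risk is not in the documents.** Section 5.1.2.1 ties the risk to initiation, in Stage 4 CKD with type 2 diabetes. It adds that the risk was not seen in six earlier CKD studies, mostly Stage 3b, or in pulmonary hypertension patients under mitigation. EAGLE draws on Alport syndrome and ADPKD trials and limits entry by BNP and by prior cardiovascular SAEs. This stands, and it keeps the point low. Two features look like support but are weak. BNP at resumption visits belongs to a list that 9.6 uses for many kinds of visit. Patients coming from bardoxolone methyl repeat the full starting regime, but one schedule serves everyone.

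**Much monitoring remains.** The rules on BNP, symptoms and suspected retention have no week limit. Section 7.3.3 requires an evaluation before dosing resumes after an extended interruption, and Appendix 1, Section 2 sends resumptions after COVID-19 infection to it for dose and visit schedule. Medical monitor or Sponsor approval is needed. After a fluid-related stop, 9.1.1 bars restart until fluid overload has been assessed and documented. A reader might infer that restarting patients go unwatched for fluid; the documents do not support that.

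**The stop rule may not lapse.** The stop sentence in 9.1.1, and a similar one in 9.9.5 that refers to daily weight increases, have no week limit of their own. The 9.1.1 sentence follows the first-8-weeks trigger, and the post-Week-8 paragraph says the opposite for a weekly gain, so lapse is the natural reading. It is not certain. Adolescents weigh daily, so the 9.9.5 sentence could still reach them, and the alert in 9.1.10 cross-refers to 9.1.1.

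**Section 9.8 carries little weight.** A reader might take its sentence as barring a return to the early weight rules. It concerns the study schedule, under serious toxicities, and does not mention weight.

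**The starting schedule has its own gap**, 56 − 45 = 11 days between the last call and the Week 8 visit. True, but daily weights cover it.

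**Conclusion.** The point holds in a limited form. For a resumption after more than 14 days off drug, or a 5 mg restart, beyond Week 8, no section returns the patient to the first-8-weeks weight rules. Adults weigh weekly and the one-day trigger does not apply. Whether a weight gain stops drug at once is ambiguous, with delay until assessment the natural reading. What is exposed is rapid gain without symptoms between contacts, which an adult may not record for up to 7 days instead of 1.

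A reader might also infer that the initiation risk is known to return on restart, or that adolescents have definitely lost the stop rule. The documents establish neither.

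The contact counts assume 2-week re-titration steps and the minimum required follow-up. The documents give neither the number of such resumptions nor an event rate after restart. Interruptions of 14 days or less resumed at the same dose are outside the point. Priority is low: SAP Section 2 records that sites were told on 10 May 2023 that development was ending, so the change matters only for the protocol as written and any further dosing under it. It is a cheap improvement to patient safety, with medium confidence.

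**What to change.** - **9.1.1 and 9.9.5:** apply daily home weights, both weight triggers and the immediate-stop instruction again, for adults and adolescents. The period is at least 4 weeks after any resumption following more than 14 days off drug, and through re-titration (up to 8 weeks) after any 5 mg restart. Four weeks covers the window in 5.1.2.1. The longer period is needed because a 5 mg restart to 30 mg still has a dose step at week 6. State the weeks to which each stop sentence applies.
- **7.3.3, 9.1.2, 9.1.9 and Appendix 1, Section 5.2:** cross-refer to the amended rule.
- **9.6:** add in-clinic weight and diary review to resumption visits.

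The cost is wording. Patients already have the scale and diary, and 9.9.5 keeps diary weights out of the eCRF, so neither data capture nor the SAP needs to change. The downside is about 24 (4 weeks) to 48 (8 weeks) extra home weights per adult resumption, none for adolescents, and some precautionary drug stops.

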9.1.10. Monitoring Growth and Sexual Development in Adolescents

Growth and sexual development will be assessed through an evaluation of height, weight, and Tanner Staging. See the Study Reference Manual for details on the Tanner staging.

Body weight should be measured daily by patients/caregivers using a provided weighing scale. Weight and height will also be measured at all site visits, as outlined in Section 9.9.4 and

Section 9.9.5. Patients should be instructed to inform the site if there is an observed weight loss of more than 3 pounds (1.4 kg) in between clinic visits (Section 9.1.1).

The medical monitor will routinely evaluate both weight and height entered into the clinical database of adolescents and will inform the investigator to initiate further evaluation if there is a weight loss of $\geq 5\%$ or lack of expected growth per growth charts.

Sexual maturity will be assessed by the investigator using Tanner Staging. If any abnormal patterns of sexual maturity are identified on evaluation of Tanner Staging, the medical monitor should be notified for additional discussion.

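### Protocol Section 9.1.1 gives contradictory stop-drug instructions for a BNP rise and for symptoms, and Section 9.9.11 restates only the conditional one

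*Protocol*

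**What the plan says.** Protocol Section 9.1.1 sets the procedures meant to limit fluid overload on bardoxolone methyl. It names three prompts.

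- **BNP.** A patient with "BNP > 100 pg/mL that represents a doubling (or more) of BNP levels from Day 1 should have an unscheduled telephone contact immediately". The next sentence sets the drug action: "If fluid retention is suspected, the patient should be instructed to stop taking study medication immediately", with medical evaluation within 1 to 2 days.
- **Weight gain, first 8 weeks.** The trigger is a "five-pound (2.3 kg) or greater increase in weight in one week or 3 pounds (1.4 kg) in one day", again followed by an immediate unscheduled call. The paragraph then ends with a sentence covering all three prompts: "Whether prompted by BNP elevations, sudden weight gain, or by the presence of clinical signs and symptoms the patient must be instructed to stop" study medication at once, with the same 1-to-2-day evaluation.
- **Symptoms.** The closing paragraph has the investigator assess symptoms of fluid overload and "determine appropriate medical management, as necessary, including whether stopping drug administration is required".

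After Week 8, a five-pound gain in one week leads to a clinic visit, and drug is not to be interrupted until the investigator has documented an assessment.

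Two other sections rely on 9.1.1. Section 9.9.5 says: "Patients will be instructed to stop administering study drug and contact the investigator if their daily weight increases per the criteria outlined" in 9.1.1. Section 9.9.11 covers telephone contacts, at which patients are asked about weight and other signs of fluid retention. It tells the site to stop drug if fluid retention is suspected, and refers to 9.1.1 for the detail.

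**The concern.** A site with a qualifying BNP result in hand finds two instructions in consecutive paragraphs of one section. One is a conditional *should*, the other an unconditional *must*. A site following the first could leave a patient on drug where the second requires a stop. A site following the second could stop drug where the first does not call for it, and 9.1.1 then bars a restart until an assessment of fluid overload is completed and documented.

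The subject matters. Protocol Section 5.1.2.1 reports an increased risk of fluid overload and heart failure hospitalization in an earlier Phase 3 trial of the drug, apparently limited to the first three to four weeks after initiation. In this study every patient starts drug at the lowest dose and is titrated, and former placebo patients take it for the first time.

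**Working it through.** No sample size, power or event count enters this point, so the check compares every place that sets a drug action for the three prompts.

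| Prompt | Instruction A | Instruction B | Same action? |
|---|---|---|---|
| Qualifying BNP rise | 9.1.1, first paragraph: stop if fluid retention is suspected | 9.1.1, second paragraph: must stop, no condition | No |
| Symptoms | 9.1.1, second paragraph: must stop, no condition | 9.1.1, closing paragraph: investigator decides whether to stop | Not as written |
| Weight gain, first 8 weeks | 9.1.1, second paragraph, and 9.9.5: stop on meeting the criteria | 9.9.11: stop if fluid retention is suspected | 9.1.1 and 9.9.5 agree; 9.9.11 differs |
| Weight gain after Week 8 | 9.1.1: no interruption before assessment | none | One rule only |

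**BNP.** If the call leads the site to suspect fluid retention, both paragraphs give the same action. If it does not, the first paragraph does not call for a stop and the second does. The second sentence names BNP explicitly, so it cannot be set aside as a rule about weight alone.

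**Symptoms.** A stop that must happen and a stop the investigator decides on can both hold only if the first is a temporary hold and the second a later decision. The section does not say that.

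**Weight gain.** Section 9.9.5 applies to daily weights and takes its criteria from 9.1.1. Both sections schedule daily weights for the first 8 weeks and weekly weights afterwards. So 9.9.5 operates in the period in which 9.1.1 also requires a stop. The only different wording is in 9.9.11. The scheduled calls fall on Days 3, 10, 21, 31, 38 and 45. All are before Day 56 (8 × 7), so all fall within the period of the unconditional weight rule.

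**Time limits.** The weight criteria are limited to the first 8 weeks. The BNP sentence and the sentence covering all three prompts state no end date. Table 5 schedules BNP at Weeks 12 and 24 and every 24 weeks thereafter, so whether the unconditional stop applies to a BNP rise after Week 8 is a practical question the text leaves open.

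**Thresholds.** With the divisor 2.205 from Section 9.9.5, 5 / 2.205 = 2.27 kg (stated as 2.3) and 3 / 2.205 = 1.36 kg (stated as 1.4). The weight criteria are internally consistent; the problem is the action attached.

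**The case against.** The best defence is that the sentence covering all three prompts carries the earlier condition forward. It closes a paragraph about unscheduled calls, repeats the earlier action including the 1-to-2-day evaluation, and may mean only that the response is the same whatever raised the suspicion. Section 9.9.11 supports this by attributing the conditional version to 9.1.1. This shows what the authors may have intended, but the sentence states no condition and replaces *should* with *must*. The reading also sits badly with 9.9.5, which has the patient stop on weight alone, before anyone has judged whether fluid is being retained.

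For symptoms, the defence is that the patient holds drug pending evaluation and the investigator then decides. That is workable, so this part is an unclear overlap rather than a flat contradiction. For weight, 9.9.11 defers to 9.1.1 and governs the scheduled calls, so the tension there is minor.

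Three stronger readings are tempting but unsupported.

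- A reader might set 9.9.5 against the post-Week-8 rule. They cover different periods, and the split is deliberate.
- A reader might infer distorted exposure or adverse event results across the approximately 230 centers. The analyses are descriptive with no comparator. SAP Section 8.2 defines exposure duration as last dose minus first dose plus 1, which a temporary stop with later resumption does not change, and takes total dose from doses dispensed minus returned, which reflects interruptions that occurred. SAP Section 8.1.2 plans a table for permanent discontinuation, not temporary interruption. No bias is shown.
- A reader might call this the drug's main risk. The documents do not rank risks.

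**Conclusion.** The point holds in narrow form. Section 9.1.1 contradicts itself on drug action after a qualifying BNP rise, is unclear for symptoms, and does not say whether either instruction continues after Week 8. For weight gain, the only defect is that 9.9.11 restates a condition that 9.1.1 and 9.9.5 do not impose in the first 8 weeks.

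The practical reach is limited to patients who meet a trigger but in whom fluid retention is not suspected, or whose drug the investigator would not stop. The documents give no count, and the planned summaries would not supply one: diary weights are not entered in the eCRF (Protocol Section 9.9.5), and the BNP threshold in SAP Section 8.4.2 is above 200 pg/mL, not above 100 pg/mL with doubling. The conclusion rests on reading the unconditional sentence as written. It is a patient-safety wording defect that should be corrected, with no demonstrated effect on the analysis.

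**What to change.** The sponsor must reconcile Sections 9.1.1, 9.9.5 and 9.9.11 so that each trigger has one action in each period. A table in the style of Table 6, which already does this for aminotransferases, would serve: trigger, period, contact, drug action, assessment. It should state whether the BNP and symptom instructions apply after Week 8, and whether the investigator's decision on symptoms precedes or follows any stop. Sections 9.9.5 and 9.9.11 should then refer to the table without restating it. Which action applies is a clinical decision for the sponsor.

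Separately, Section 9.1.10 needs an editorial correction. It cites 9.1.1 for a "weight loss of more than 3 pounds (1.4 kg) in between clinic visits (Section 9.1.1"), but 9.1.1 has only weight-gain criteria. Its daily weighing of adolescents, given without an end date, should be reconciled with the weekly schedule after Week 8.

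The cost is protocol wording. SAP Section 2 records that the decision to discontinue clinical development was communicated to sites on 10 May 2023. If no further dosing is planned, an amendment has little prospective value, and the clinical study report should disclose the ambiguity.
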